2.6 Sample Size

For the primary efficacy analysis in this trial, it is assumed that the mean change from Baseline in Hb for vadadustat will be the same as for the active control darbepoetin alfa, and the common standard deviation for the mean change from Baseline is assumed to be 1.2 g/dL. Noninferiority will be established based on a 2-sided 95% confidence interval (CI) for the difference between vadadustat QD group and darbepoetin alfa group and using a noninferiority margin of -0.75 g/dL. With these assumptions and approximately 100 subjects per treatment group, the noninferiority test will have > 90% power with consideration of a 30% drop out rate. Same assumptions and sample size calculations will be applied to the difference between vadadustat TIW group and darbepoetin alfa group. After the noninferiority of vadadustat QD is demonstrated, the noninferiority of vadadustat TIW group to darbepoetin alfa group will be tested hierarchically with 2-sided significant level of 0.05.

2.7 Efficacy

Treatment comparisons in efficacy analyses are between vadadustat QD and darbepoetin alfa, and between vadadustat TIW and darbepoetin alfa.

For clarity, this SAP uses the word "mean" to refer to averages over the study groups and "average" to refer to the within-person average during specified evaluation periods.

The primary efficacy endpoint is defined as the Hb change from Baseline (average pretreatment Hb) to the average Hb from Weeks 20 to 26 (inclusive).

The primary efficacy objective is to first show that vadadustat QD is noninferior to darbepoetin alfa within the noninferiority margin. Noninferiority will be established based on a margin of -0.75g/dL (for vadadustat minus darbepoetin alfa). If vadadustat QD meets the noninferiority criterion, then the next objective is to show that vadadustat TIW is noninferior to darbepoetin alfa within the noninferiority margin.

If the lower limit of the 2-sided 95% confidence interval for the difference between the mean Hb change from baseline to Weeks 20 to 26 in the vadadustat group and the mean Hb change from baseline in the darbepoetin alfa group is above zero, superiority will have been established and the finding will be interpreted as providing evidence of a greater change from baseline in Hb for vadadustat relative to the control arm. Because the same 95% confidence interval is used to the superiority test, no adjustment for multiplicity is needed.

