## 2.4 Known and Potential Risks and Benefits

Please see the vadadustat IB for additional information.

Trials of injectable ESAs in patients with anemia secondary to NDD-CKD or DD-CKD have demonstrated an increased risk of CV events associated with higher Hb targets. Post-hoc analyses performed by the Food and Drug Administration (FDA) and others have shown an association between these adverse outcomes and supraphysiologic serum EPO levels and/or Hb oscillations and overshoots. In studies to date, oral vadadustat daily increased mean Hb with few excursions above the target range. In addition, serum EPO levels remained well below those reported with ESAs in the literature. As a result, there is the potential for the investigational drug vadadustat to provide an effective and safe therapeutic option for the treatment of renal anemia.

In addition, vadadustat may enhance iron metabolism and transport. phase 1 and phase 2 studies have demonstrated a consistent dose-dependent increase in TIBC and decrease in ferritin and hepcidin. Mechanistic studies have demonstrated that HIF stabilization downregulates the iron absorption regulator hepcidin, and upregulates the iron-mobilizing regulators ferroportin and transferrin (and its receptor). Potential clinical benefits include enhanced erythropoiesis and decreased exogenous iron requirements.

In nonclinical safety studies, the main findings originated from an exaggerated pharmacological response that results in increased erythropoiesis, polycythemia, blood hyperviscosity, and the formation of fibrin thrombi in multiple organs. Early mortality noted in the mouse and rat and moribundity in the dog were due to the sequelae associated with polycythemia. These findings were reproducible across species and

studies, dose-dependent and showed reversibility. Dose-limiting toxicity in the exploratory toxicology studies was due to hemoglobinuric nephropathy (rat) and emesis associated with body weight loss (dog).

In completed phase 1 clinical studies of vadadustat in healthy subjects, there were low numbers of treatment-emergent AEs. The most frequently reported AEs were in the gastrointestinal disorders (ie, nausea, diarrhea, abdominal pain, flatulence, dyspepsia) and nervous system disorders (ie, headache, dizziness) SOC. The majority of AEs were mild to moderate in severity.

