## 4 Trial Design

### 4.1 Type/Design of Trial

This is a phase 3b, randomized, open-label, active-controlled trial of vadarustat versus darbepoetin alfa for the maintenance treatment of anemia in hemodialysis subjects, after conversion from ESA therapy.

Following a Screening period of up to 8 weeks (56 days), subjects who meet all eligibility criteria will be randomized 1:1:1 to vadarustat QD, vadarustat TIW, or darbepoetin alfa. Target enrollment in this trial is an estimated 300 subjects at up to 150 investigative sites in the US and Europe ([Figure 1.2-1](#)).

Subjects will be randomized at the Baseline Visit using an Interactive Web Response (IWR) system to receive either vadarustat QD, vadarustat TIW, or darbepoetin alfa.

Randomization will be stratified with respect to:

- Geographic region (US versus Europe, approximately 90 subjects in Europe).
- Mean weekly darbepoetin alfa dose (or ESA equivalent) calculated over a period of 8 weeks prior to Screening Visit 2:
  - Low darbepoetin alfa dose group ( $\leq 0.45 \mu\text{g/kg/week}$ ).
  - High darbepoetin alfa dose group ( $> 0.45$  and  $\leq 1.5 \mu\text{g/kg/week}$ ).

In each stratum, there will be 3 arms: vadadustat QD, vadadustat TIW, and darbepoetin alfa.

Following screening and randomization, there will be 2 periods during the trial:

- **Conversion and Maintenance Treatment Period (Weeks 0 to 52):** conversion to investigational medicinal product (IMP) for maintaining Hb (Weeks 0 to 20), primary efficacy evaluation (Weeks 20 to 26), and secondary efficacy evaluation (Weeks 46 to 52).
- **Safety Follow-up Period (Early Termination [ET] and Follow-up):** post-treatment Safety Follow-up Visit (ET/End of Treatment [EOT] + 4 weeks) (in person).

Individual subjects will participate in total trial duration of approximately 64 weeks.

A structured exit interview may be conducted at the EOT Visit at a subset of sites. Hemoglobin will be assessed with a complete blood count (CBC) through the central laboratory for dose adjustments and efficacy and safety evaluations.

**The aim of the dosing strategy is to maintain Hb levels of 10.0 g/dL to 11.0 g/dL in the US and 10.0 g/dL to 12.0 g/dL in Europe.**

For subjects assigned to vadadustat, the initial dose of vadadustat will depend on mean weekly darbepoetin alfa dose (or equivalent) calculated over a period of 8 weeks prior to Screening Visit 2 as follows:

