9.2.4 Analysis of Change from Baseline in Hb to the Primary Efficacy Period

The primary analysis will use multiple imputation with ANCOVA as the substantive model and will be performed in the randomized population.

All intercurrent events will be handled by treatment policy strategy (see [Section 9.1](#)). Unobserved data after intercurrent events, including hemoglobin outcomes and any covariates to be used in the models, will be imputed with randomized subjects using multiple imputation under fully conditional specification (FSC) method. Under the assumption of FSC, data for each variable with missing values will be imputed with a separate regression model allowing for all available data to be used in the imputation process. For continuous variables, the regression method will be used for imputations. For categorical variables, logistic regression models will be used for binary outcomes, and nominal response logistic regression for nominal responses.

An ANCOVA model will be used to compare the mean change from baseline in Hb between 2 treatment groups with the complete dataset from multiple imputation. The ANCOVA model will contain treatment group, baseline Hb level, and the 2 stratification factors (geographic region and mean weekly darbepoetin alfa dose prior to Screening Visit 2) as predictor variables. The stratification factor assignments at randomization will be used in the analysis.

The data will have shown noninferiority of vadadustat if the lower bound of the 95% confidence interval for the difference in estimated change from baseline in the 2 groups (vadadustat minus darbepoetin) exceeds the noninferiority margin of -0.75g/dL. This ensures a 1-sided alpha of 0.025 for the primary analysis. If the lower limit of the 2-sided 95% confidence interval for the difference between the mean in the vadadustat group and the mean in the darbepoetin alfa group is above zero, superiority will have been established and the finding will be interpreted as providing evidence of a greater change from baseline in Hb for vadadustat relative to the control arm.

The procedure of primary analysis follows these steps:

- 1) Missing data will be imputed separately for each treatment group using FSC method with 100 imputed datasets and 40 iterations from PROC MI. The SAS codes of PROC MI with outcome variables and covariates will be as follows.

[REDACTED]

[REDACTED]

[REDACTED]

[REDACTED]

[REDACTED]

[REDACTED]

[REDACTED]

[REDACTED]

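### The SAP declares superiority on mean Hb from a lower 95% limit above zero, with no upper bound and no link to the target-range result, although both arms are titrated to the same range

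*SAP*

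**What the plan says.** SAP 2.7 and SAP 9.2.4 take the same two-sided 95% interval that serves the noninferiority test and attach a second conclusion to it. If the lower limit for vadadustat minus darbepoetin alfa is positive, "superiority will have been established and the finding will be interpreted as providing evidence of a greater change from baseline in Hb for vadadustat", compared with control. In SAP 9.2.4 the condition is that the lower limit for the vadadustat mean minus the "mean in the darbepoetin alfa group is above zero, superiority will have been established". Neither section caps the difference or the achieved Hb, and neither refers to the target-range endpoint.

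The rest of the plan describes a maintenance trial:

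- Protocol 4.1: "The aim of the dosing strategy is to maintain Hb levels of 10.0 g/dL to 11.0 g/dL in the US". For Europe the range is 10.0 to 12.0 g/dL. SAP 2.3 gives the same ranges.
- Protocol Table 6.1.1.2-1 applies one adjustment guideline to both drugs. Hb above 11.0 g/dL (US) or 12.0 g/dL (Europe) calls for dose reduction or interruption. SAP 2.5 says darbepoetin alfa dosing incorporates that guideline, alongside the label and investigator discretion.
- Protocol 9.1 and 9.4.1.1.2 plan noninferiority only. Superiority on mean Hb is also absent from the eight-step order in SAP 9.5. SAP section 1 says the SAP prevails where the two documents differ.

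**The concern.** If both drugs do their job perfectly, both arms sit in the same range and the difference is zero. A positive difference can arise in at least three ways: vadadustat holds Hb in range while control falls short, both arms are in range at different levels, or vadadustat runs above range. Only the first is clearly better maintenance, and in an open-label trial with discretionary dosing it could also reflect under-titration of the control.

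The rule sees only the lower confidence limit, so it gives all three the same label. At stake is what the report may say about the primary endpoint. An arm whose Hb runs high could be described as both noninferior and superior, with the excess visible only in other tables. This is a question of meaning and would remain even if the type I error were fully controlled.

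**Working it through.** **Inputs from SAP 2.6.** Common SD 1.2 g/dL; about 100 per arm; 30% dropout, so 100 × 0.70 = 70 evaluable; noninferiority assessed "using a noninferiority margin of -0.75 g/dL"; planning difference zero, since "it is assumed that the mean change from Baseline in Hb for vadadustat will be the same as for the active control darbepoetin alfa". The error level is from SAP 9.2.4: "This ensures a 1-sided alpha of 0.025 for the primary analysis".

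**Standard error.** SE = 1.2 × √(2/n) = 0.203 (n = 70) or 0.170 (n = 100).

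**The plan's own power figure.** Power at true difference 0 is Φ(0.75/SE − 1.96).

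- n = 70: Φ(3.698 − 1.96) = 95.9%.
- n = 100: Φ(4.419 − 1.96) = 99.3%.

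The stated power above 90% is reproduced.

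**When the superiority rule fires.** It needs an observed difference above 1.96 × SE, which is 0.398 g/dL (n = 70) or 0.333 g/dL (n = 100). At true difference d the probability is Φ(d/SE − 1.96):

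| True difference (g/dL) | 70 per arm | 100 per arm |
|---|---|---|
| 0 | 2.5% | 2.5% |
| +0.5 | 69% | 84% |
| +0.75 | 96% | 99% |

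At +0.5, noninferiority passes with probability Φ((0.5 + 0.75)/SE − 1.96), which is above 99.99% for both sizes.

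**Same difference, different meaning.** Take a US difference of +0.5 g/dL. Control 9.75 and vadadustat 10.25 puts the control mean below range. Control 10.25 and vadadustat 10.75 puts both means in range. Control 10.75 and vadadustat 11.25 puts the vadadustat mean above range. The rule treats the three alike.

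**What +0.5 does to the US target-range result.** The documents give no control mean and no SD for the period-average Hb level; the 1.2 is for the change. I assume a normal distribution, control means of 10.0 to 10.75 and SD 1.0 to 1.2. In range is Φ((11 − m)/SD) − Φ((10 − m)/SD), and above range is 1 − Φ((11 − m)/SD). For example, with m = 10.5 and SD 1.0, above range is 1 − Φ(0.5) = 31%; shifted to 11.0 it is 1 − Φ(0) = 50%.

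| Control mean | SD | In range, control → shifted | Above range, control → shifted |
|---|---|---|---|
| 10.0 | 1.0 | 34% → 38% | 16% → 31% |
| 10.0 | 1.2 | 30% → 32% | 20% → 34% |
| 10.25 | 1.0 | 37% → 37% | 23% → 40% |
| 10.25 | 1.2 | 32% → 32% | 27% → 42% |
| 10.5 | 1.0 | 38% → 34% | 31% → 50% |
| 10.5 | 1.2 | 32% → 30% | 34% → 50% |
| 10.75 | 1.0 | 37% → 30% | 40% → 60% |
| 10.75 | 1.2 | 32% → 27% | 42% → 58% |

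The in-range change runs from about +4 to −8 points, and its sign depends on the control mean. The above-range proportion rises by about 14 to 20 points in every row.

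**Europe (upper limit 12).** With a control mean of 10.5, the in-range proportion rises from 63% to 68% (SD 1.0) or from 56% to 60% (SD 1.2). With a control mean of 11.0 those changes reverse.

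**The case against.** **The SAP limits its own reading.** It interprets the finding as a greater change in Hb, claims neither better maintenance nor clinical benefit, and defines superiority on the target range separately in 9.4.1. That is a fair description, and a reader should not infer that the SAP claims a clinical advantage. The word 'superiority' on the primary endpoint is still what a report would carry. If only a higher mean is intended, the text can say so.

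**Overshoot is examined elsewhere.** The in-range proportion is tested for noninferiority with a −15% margin at steps 5 to 8 of SAP 9.5. SAP 10.2 gives stratified risk differences for Hb above 11 (US), 12, 13 and 14 g/dL and for rapid rises. SAP section 11 analyses the primary endpoint by regional target. This softens the problem, but none of it conditions the superiority statement.

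**A higher mean can be an improvement.** This stands. With a US control mean of 10.0 or a European one of 10.5, a +0.5 shift raises the in-range proportion. A reader might infer that most superiority declarations would come with a worse target-range result. That holds only for certain control means, such as 10.5 in the US, and the documents give none.

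**No multiplicity adjustment is needed on the same interval.** SAP 2.7 makes this argument. It concerns error rates and leaves the meaning of the label untouched.

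**The cardiovascular background does not transfer directly.** Protocol 2.4 reports "an increased risk of CV events associated with higher Hb targets" in trials of injectable ESAs. Here both arms share a target, and the same section reports few excursions on vadadustat. The point rests on the shared range and the dosing guideline, not on that evidence.

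**Conclusion.** The concern holds as a defect in what the SAP allows to be concluded. The noninferiority test and its power are unaffected.

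Two stronger readings are not supported. First, a merely higher mean does not trigger the rule: an observed difference up to about 0.33 to 0.40 g/dL does not qualify, and under the planning assumption of no difference the rule fires about 2.5% of the time. Second, overshoot does not by itself lead to a superiority declaration: a small overshoot, or overshoot in both arms, would usually not trigger it.

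What remains is a rule that fires 69% to 84% of the time at a true +0.5 g/dL and cannot tell why the difference arose. Those probabilities use only the plan's SD and sample sizes. The target-range figures rest on the assumed control means, SDs and normality. Under them the in-range proportion may move either way, while the US above-range proportion rises by about 14 to 20 points throughout.

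**What to change.** In SAP 2.7 and SAP 9.2.4, replace the superiority sentence with text such as:

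> If the lower limit exceeds zero, mean Hb is higher on vadadustat. This is not a superiority claim and is read together with the proportions of subjects within and above the regional target range.

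Carry the same statement as a footnote to the primary-endpoint table.

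Keep superiority wording only for the in-range proportion in SAP 9.4.1, where a higher value does mean better maintenance. That section refers to SAP 9.5 for its superiority test, but the SAP 9.5 list contains only noninferiority steps. Either add the test to the order or label it descriptive.

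An upper limit on the mean difference is optional, and the documents give no basis for a particular value.

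The cost is a change of wording: no new data, no new primary analysis and no change to dosing. The sponsor gives up a superiority label on mean Hb that the protocol never planned.

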9.3 Secondary Efficacy Endpoints: Definitions and Analyses

The key secondary efficacy endpoint will be formally analyzed once the non-inferiorities have been established in the primary endpoint for vadadustat QD and TIW regimens.

Mean change in Hb value between Baseline and the secondary evaluation period (average Hb from Weeks 46 to 52) will be analyzed using the same methodology as specified for the primary efficacy endpoint. Sensitivity analyses like those of the primary efficacy endpoint will be performed.

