9.4 Other Efficacy Endpoints: Strategies for Analysis

Except for specifying the analysis population, other efficacy endpoints analyses will be performed using the randomized and full analysis population, with the assigned treatment as described in [Section 3.1](#). There will be no correction for multiplicity for these endpoints.

9.4.1 Proportion of Subjects Having Average Hb Values within the Target Range during the PEP (Weeks 20 to 26)

All subjects will be defined as either being in their geography-specific target range (see [Section 2.3](#)) in Weeks 20 through 26 (“yes”) or not (“no”), based on the average Hb value during the three visit windows in Weeks 20 through 26. Subjects with no Hb value in the PEP value will be treated as missing. To ensure uniformity across all analyses, the missing binary outcomes will be computed from the imputed complete dataset in primary analysis (see [Section 9.1.4](#)) [Ratitch, 2013].

The proportion of subjects within target range will be calculated, and a 95% confidence interval of the proportion will be performed by treatment group.

A Mantel-Haenszel estimation of risk difference stratified by the baseline strata will be conducted, and the corresponding 2-sided 95% confidence interval for the risk difference will be calculated. Noninferiority will have been established if the lower limit of the confidence interval is above -15% when tested per the testing procedure ([Section 9.5](#)).

If the lower limit of the 2-sided confidence interval for the risk difference is above zero, superiority will have been established and the finding will be interpreted as providing evidence of a higher proportion of subjects being within the target range for vadadustat relative to the control arm when tested per the testing procedure ([Section 9.5](#)).

The associated odds ratio and corresponding 2-sided 95% confidence interval will also be calculated.

The analysis of proportion of subjects within target range follows these steps:

9.4.2 Proportion of Subjects Having Average Hb Values within the Target Range during the SEP (Weeks 46 to 52)

Proportion of subjects having average Hb values within the target range during the SEP (Weeks 46 to 52) will be analyzed using the same methodology as specified for the PEP (see Section 9.4.1).

9.4.3 Proportion of Subjects Receiving IV Iron Therapy from Baseline to Week 52

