9.5 Study Level Type I Error Control

The study-wise type I error control for multiple testing of efficacy endpoints is controlled at 0.05 level, two-sided by using hierarchical testing procedure. The order of hierarchy is listed below. Upon the demonstration of the non-inferiority of the primary endpoint of vadadustat QD vs. darbepoetin alfa for the change in average Hb between baseline and the PEP, the non-inferiority of the other primary endpoint of vadadustat TIW vs. darbepoetin alfa for the change in average Hb between baseline and the PEP will be examined with pre-specified margin. If it meets the noninferiority margin, the secondary efficacy endpoints in the list will be examined against the pre-specified statistical criteria and so on. In other words, an endpoint will only be tested against pre-specified statistical criteria when the previous endpoint meets statistical criteria. Once an endpoint did not meet the statistical criteria, any endpoints after it will not be formally tested. The hierarchical testing order will be as follows:

1. Noninferiority of vadadustat QD vs. darbepoetin alfa for the change in average Hb between baseline and the PEP (primary efficacy endpoint).
2. Noninferiority of vadadustat TIW vs. darbepoetin alfa for the change in average Hb between baseline and the PEP (primary efficacy endpoint).
3. Noninferiority of vadadustat QD vs. darbepoetin alfa for the change in average Hb between baseline and the SEP (secondary efficacy endpoint).
4. Noninferiority of vadadustat TIW vs. darbepoetin alfa for the change in average Hb between baseline and the SEP (secondary efficacy endpoint).
5. Noninferiority of vadadustat QD vs. darbepoetin alfa for the proportion of subjects having average Hb values within the target range during the PEP (other efficacy endpoint).
6. Noninferiority of vadadustat TIW vs. darbepoetin alfa for the proportion of subjects having average Hb values within the target range during the PEP (other efficacy endpoint).
7. Noninferiority of vadadustat QD vs. darbepoetin alfa for the proportion of subjects having average Hb values within the target range during the SEP (other efficacy endpoint).

8. Noninferiority of vadadustat TIW vs. darbepoetin alfa for the proportion of subjects having average Hb values within the target range during the SEP (other efficacy endpoint).

10 Safety Analyses

All analyses of safety data will use the safety population.

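### Superiority on the primary hemoglobin endpoint can be declared for either vadadustat arm with no adjustment, outside the SAP's study-wise error control

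*SAP*

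**What the plan says.** SAP 2.7 names two efficacy comparisons, vadadustat QD and vadadustat TIW, each against darbepoetin alfa. After the noninferiority rule it adds a superiority rule: the lower limit of the 95% interval must be above zero. It then states: "Because the same 95% confidence interval is used to the superiority test, no adjustment for multiplicity is needed".

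SAP 9.2.4 repeats the rule, saying that in this case "superiority will have been established and the finding will be interpreted as providing evidence of a greater change from baseline in Hb for vadadustat". Just before, about the noninferiority criterion, it says: "This ensures a 1-sided alpha of 0.025 for the primary analysis".

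On the order of the arms, SAP 2.6 says that once QD noninferiority is shown, "the noninferiority of vadadustat TIW group to darbepoetin alfa group will be tested hierarchically with 2-sided significant level of 0.05". SAP 9.5 states the overall claim: "The study-wise type I error control for multiple testing of efficacy endpoints is controlled at 0.05 level, two-sided by using hierarchical testing procedure". Its rule is that "an endpoint will only be tested against pre-specified statistical criteria when the previous endpoint meets statistical criteria". The list has eight steps: Hb change at Weeks 20-26, Hb change at Weeks 46-52, and target-range proportion in each of those periods, each for QD and then TIW. Every step is noninferiority.

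The protocol (9.1 and 9.4.1.1.2) plans only noninferiority for the primary endpoint. The superiority claims therefore come from the SAP, which by its Section 1 prevails where the two differ.

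**The concern.** Moving from noninferiority to superiority on one interval costs no error within one arm. SAP 2.7 applies that argument to two arms that share a control and places no order or gate between the two superiority claims. TIW noninferiority also opens at full alpha once QD noninferiority is met, whether or not QD superiority is met. The sequence therefore branches, and full alpha is used on both branches.

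At stake is a statement that an arm has been shown superior, presented as error-controlled when the chance of at least one such false statement is nearly double the rate for a single comparison.

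Three wording gaps go with it:

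- **Target range.** SAP 9.4.1 (and 9.4.2, which follows it) makes target-range superiority a finding for "vadadustat relative to the control arm when tested per the testing procedure" of Section 9.5. That section has no superiority step, so it is unclear whether any such claim is allowed.
- **Weeks 46-52.** SAP 9.3 says the key secondary endpoint "will be analyzed using the same methodology as specified for the primary efficacy endpoint". It is unclear whether that carries the superiority rule with it.
- **Other endpoints.** SAP 9.4 says the other endpoints receive no multiplicity correction, while steps 5-8 of 9.5 put two of them in the controlled sequence.

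**Working it through.** **Inputs.** SAP 2.6: SD 1.2 g/dL, margin -0.75 g/dL, true difference 0, about 100 per arm, 30% dropout. SAP 2.1: 1:1:1 allocation. SAP 9.2.4: one-sided 0.025, critical value 1.96.

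**1. The plan's own power figure.** With 70 evaluable per arm, SE = 1.2 × √(2/70) = 0.203, and power = Φ(0.75/0.203 − 1.96) = Φ(1.74) = 95.9%. With 100 per arm, SE = 0.170 and power is 99.3%. The stated figure of more than 90% reproduces.

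**2. One comparison.** If the true difference is 0, only the superiority null is true, and it is rejected with probability 0.025. If the true difference is -0.75, both nulls are true, but a superiority claim implies a noninferiority claim, so the chance of any error is again 0.025. The SAP's reason is right for one arm.

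**3. Two arms, shared control.** The correlation of the two test statistics is ρ = n_active / (n_active + n_control), which is 0.5 for equal arms. With both true differences zero, the chance of at least one false superiority claim is 1 − Φ₂(1.96, 1.96; ρ).

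| Analysed sizes | ρ | Chance of at least one false claim |
|---|---|---|
| Equal arms | 0.500 | 4.54% |
| Control 100, each active arm 70 | 70/170 = 0.412 | 4.65% |
| Control 70, each active arm 100 | 100/170 = 0.588 | 4.40% |

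For reference, two independent tests would give 1 − 0.975² = 4.94%.

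**4. With the noninferiority gates.** A simulation of 4,000,000 draws (SD 1.2, margin -0.75) tested TIW only after QD noninferiority:

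| True QD, true TIW | False claims counted | As the SAP stands | Order: QD NI, TIW NI, QD superiority, TIW superiority |
|---|---|---|---|
| 0, 0 | Superiority, either arm | 4.53% (n = 70 and n = 100) | 2.5% |
| 0, -0.75 | QD superiority or TIW noninferiority (NI) | 4.53% | 2.5% |
| -0.75, 0 | QD noninferiority or TIW superiority | 2.5% | not run |

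In the first row the gates give almost no protection, because noninferiority is met 96-99% of the time when the true difference is zero (step 1). The second row is the branching problem: full alpha is used on QD superiority and again on TIW noninferiority. In the third row the QD gate works.

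**5. Why a fixed order suffices.** In one ordered chain, a false claim requires rejecting the first true null reached, and that has probability at most 0.025. The argument does not depend on the number of preceding steps, so it also covers superiority tests placed after all eight.

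**The case against.** The strongest reply is that SAP 9.5 ties its control statement to a closed list. Superiority is not on it, so it could be read as outside the formal family and thus informal. The text does not support that reading: it says superiority will have been established and offers a multiplicity justification, which a descriptive result would not need. If descriptive is what is meant, saying so is one of the two fixes.

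A second reply is that the 0.025 sentence in 9.2.4 belongs to the noninferiority rule, where it is true. That is correct, and the sentence is not evidence of a contradiction. The finding does not need it: 2.5% one-sided is what a two-sided 95% interval gives for any single claim in one direction. For the same reason 4.5% should not be set against the two-sided 0.05 of 9.5. The two-sided counterpart, a false finding in either direction for either arm, is 9.1%.

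A third reply is that the consequence is small. Treatment aims to hold Hb within a range, the primary objectives are noninferiority, and no listed step would change. That stands and limits the weight of the point, but it does not make the rule correct.

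A fourth is that the figures assume both arms are tested for superiority with no gate between them. They do. The SAP states no gate, so this is its plain reading.

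Two of the wording gaps are mild. The phrase in 9.3 need not import a superiority claim, and the sentence in 9.4 could be read as describing the interval level. Each needs only a clarifying phrase.

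**Conclusion.** The concern holds. The justification in SAP 2.7 covers a single comparison but is applied to two. The chance of at least one false superiority claim on the primary endpoint is about 4.5% one-sided, roughly 1.8 times the 2.5% for one comparison (4.54/2.5). This assumes both true differences are zero, normal test statistics, and no superiority gate between arms; unequal analysed arms move it only between 4.40% and 4.65%. The same 4.53% applies to false QD superiority or false TIW noninferiority when QD is truly equal and TIW lies at the margin. The eight noninferiority steps are controlled as written, and no noninferiority conclusion is affected. This should be fixed, but it does not threaten the primary objective. The three wording gaps are secondary.

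**What to change.** In SAP 9.5, choose one of two courses.

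- **(a) Formal superiority.** Add QD superiority and then TIW superiority on the primary endpoint as steps 9 and 10, each tested only if every earlier step succeeds. Any other superiority claim that is wanted, such as target range, must be listed after these. The position matters: if superiority were inserted after step 2, QD superiority would fail about 97.5% of the time under the planned zero difference and would block the present steps 3-8.
- **(b) Descriptive superiority.** State that superiority results are descriptive, and replace the wording in 2.7, 9.2.4 and 9.4.1 that says superiority will have been established.

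Under either course:

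- Delete the sentence on adjustment in 2.7, or limit it to a single comparison.
- State in 9.3 whether superiority is claimed at Weeks 46-52.
- In 9.4, exempt the two target-range endpoints from the statement that no correction is made.

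The cost is SAP wording. Under (a), superiority becomes harder to reach, since all eight noninferiority steps must succeed first. Under (b), it is no longer a formal claim. The noninferiority tests, sample size and power are unchanged.
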